**Table 1. Delivery of the Intervention Across Clinics**

	2018				2019				2020			
	Q1	Q2	Q3	Q4	Q1	Q2	Q3	Q4	Q1	Q2	Q3	Q4
First wave												
Second wave												
Third wave												

**Informed Consent.** Once patients are cleared to participate in the study by their doctor, the CHW or research coordinator will review the informed consent form with them at the clinic, and the patient will be asked to give their written informed consent to participate in the clinical trial.

**Study Intervention.** We will test the effectiveness of a culturally sensitive, evidence-based, multi-component, behavioral program for treating obesity called Health-Smart.™ This program will be implemented for 6 months in 20 UF Health Jacksonville primary care clinics by CHWs with Black women patients who have obesity, and followed by either of two physician-implemented behavioral counseling programs that are applied quarterly over 12 months to prevent weight regain. CHWs will be hired by the primary care network as UF OPS employees and trained to be staff members of the clinic to which they are assigned. The CHWs will also receive extensive training on the Health-Smart program by the PI ([name]) and her team prior to program implementation. A brief description of each intervention component used in this study is as follows:

**Measurement Session 1.** The patient's baseline biometric data (weight, height, blood pressure) will be measured by an MA at their physician's clinic. Additionally, blood will be drawn to assess total cholesterol, LDL- cholesterol, HDL-cholesterol, triglycerides, glucose, and HbA1c if this has not been done in the last 30 days or during the physician screening visit. These data will be entered into the Health Data Log. Every attempt will be made to obtain the blood sample while the patient has been fasting. However, when that is not feasible, it will be noted in the form that the patient has not been fasting. Next, a trained CHW at the patient's primary care clinic will provide a battery of questionnaires to be filled out on site (see Questionnaire/Instruments section for descriptions). The research coordinators assigned to the clinics for this project will input the patients' biometric and lab data from the Health Data Log form and store it in the dedicated IRB research drive to prepare the data for analyses. Patient name, the date the measurement was taken, and the name of the clinic they are assigned to will also be included in the database.

**Participation in the 6-month Health-Smart weight loss program.** Within two months after completing Measurement Session 1, patients will begin the Health-Smart weight loss program. ***The 6-month clinic-adapted Health-Smart intervention is part of both comparators*** and includes the following components/strategies: (a) assessment of each

participant's motivators of and barriers to health-smart behaviors using the Motivators of and Barriers to Health-Smart Behaviors Inventory—which has been published by the study PI; (b) coaching by a trained CHW that involves using the inventory-identified motivators and barriers to facilitate the patient participant's goal-setting and identification of strategies to achieve their goals, teaching participants to monitor selected health-smart goals and related goal attainment strategies, reviewing the standard goals for all patients that include 5% weight loss and increasing or maintaining steps walked to meet the 10,000 steps per day walking goal, and facilitating a patient-family member/friend discussion during which the patient asks the family member/friend to engage in behaviors that will support the patient in implementing her health-smart goal achievement strategies; (c) three months of weekly group sessions and then 3 months of bi-weekly group sessions; (d) 150 minutes of physical activity each week via patient participant-arranged or CHW-arranged activities such as group walks and individual walking to achieve 10,000 steps per day, and/or other self-selected moderate physical activities, and documentation of the physical activities in addition to documenting steps walked. Furthermore, the walking steps should begin with any number of steps that can be walked without any physical discomfort (e.g., pain, difficulty breathing) and then gradually increased by a number of steps that can be walked without any physical discomfort. Additionally, for participants who cannot walk at all, the physical activity goal is to engage in any physical activity up to 150 minutes per week that does not cause any physical discomfort. During at least one of the sessions in the Health-Smart intervention, patient participants will be given the opportunity to anonymously or directly ask health-related questions to a panel of health experts (e.g., dietitians) and Black women community members who have lost weight and maintained this weight loss.

The first week of Health-Smart will involve having a trained CHW, employed by the clinic, to help participating patients set health-smart behavior goals and weight-loss goals and identify strategies for achieving these goals using the Motivators of and Barriers to Health-Smart Behaviors Inventory (MB-HSBI). The CHW will review the standard goals for all patients that include 5% weight loss and increasing or maintaining steps walked to meet the 10,000 steps per day walking goal. Patients are will be asked to bring a family member or friend support person to the first session of Health-Smart only. This support person will be asked to make a commitment to help achieve the patient's health-smart goals.

Patients will attend the CHW-led Health-Smart weekly 1 ½- to 2-hour group sessions for 3 months and then bi-weekly group sessions for another 3 months. During these sessions, patients will be weighed. Patients will view and discuss segments of a Health-Smart DVD that show culturally diverse families and community members, licensed physicians and other health care providers discussing health-smart behaviors and “real world” strategies for promoting these behaviors. Patients will be given a Health-Smart Resource Guide that is a supplement to the Health-Smart DVD—a guide that contains more detailed information about the discussed health-smart behaviors and “real world” strategies for promoting these behaviors. Patients will be encouraged to review sections of the Health-Smart Resource Guide that are relevant to each week’s group discussion. Patients will also be encouraged to follow a reduced-calorie eating plan to promote a 5% loss of their current body weight during the 6-month weight-loss intervention. Sample reduced-calorie meal plans that provide approximately 1200 kcals from a well-balanced diet from a variety of foods emphasized in the 2015 Dietary Guidelines for Americans will be provided to patients. They will also participate in 150 minutes of physical activity each week - either on their own or arranged by

a trained Community Health Worker. Throughout the 6-month Health-Smart program, patients will be using a Food and Activity Diary to record their steps walked using a pedometer that will be provided to them as well as document other physical activity performed during each week. They will also be recording food and beverages consumed daily.

**Measurement Session 2.** After the completion of the 6-month Health-Smart weight loss program, patients' weight, height, blood pressure will be measured by a Medical Assistant at their physician's clinic. Additionally, patients' blood will be drawn to assess their total cholesterol, LDL- cholesterol, HDL-cholesterol, triglycerides, glucose, and HbA1c and they will complete the questionnaires previously completed as part of Measurement Session 1. The research coordinators assigned to clinics will input the patients' biometric and lab data from the Health Data Log form and store it in the dedicated IRB research drive.

**Weight Loss Maintenance Support from Primary Care Physician.** During the 12 months after completing the 6-month Health-Smart weight loss program, patients will have quarterly visits with their physician (at no charge to the patients) so that the physician can provide counseling and support to the patients that is designed to help the patients continue to lose weight or maintain the weight loss that resulted from participating in the Health-Smart weight loss program. In this phase, two different 12-month weight maintenance programs implemented by physicians will be compared (PCCS-WLM program and SB-WLM program). Both the patient and the CHW will be blinded on which program the patient will be participating in. The clinics will be randomly assigned to one of these two programs. The PCCS-WLM program (Comparator 1) will be implemented by the physicians of the participating patients at 10 clinics in this study, and the SB-WLM (Comparator 2) will be implemented by the physicians of participating patients at a separate set of 10 clinics in the study. Both of these programs consist of patient-physician clinical encounters every three months over a 12-month period, during which physicians in each program will review each of their participating patient's clinic-tracked weight/BMI and implement evidence-based provider behavioral counseling strategies for weight-regain prevention with each of these patients. A summary form that includes the patient's weight loss goals and health-smart goals will be provided to the physician prior to their first maintenance visit.

**Focus Groups.** Focus groups with Black women with weight concerns will be performed to identify specific ways providers can demonstrate cultural sensitivity that will be among the foci of the physician training for the PCCS-WLM program (Comparator 1). A minimum of two but no more than four focus groups will be conducted before the end of 2018. Each group will include 6 to 10 participants per focus group. Each participant will receive a \$30 gift card for their participation and will be required to complete a gift card receipt form that includes their name, social security number, address, and phone number. Focus group participants will be recruited from the general population through disseminating flyers about these groups at local clinical settings (e.g., the participating clinics and at hospitals and walk-in health care sites), community settings (e.g., local Black churches), and meetings that are attended by large numbers of Black women. The snowball technique will also be used to recruit Black women to participate in the focus groups. This technique involves having individuals who agree to be research (focus group) participants help recruit other focus group participants. Focus groups will be held at UF Health, or at an identified site closest to the participating women.

A focus group guide has been created to standardize what information will be collected during each session. Black women group facilitators for each focus group will follow the guide, which includes a standard introduction and focus group questions. These group facilitators will have had experience in conducting focus groups and will be trained in conducting the focus groups for this study. Each focus group discussion will be audio-recorded with notes taken on key issues by graduate students supervised by the one of the members of the research team. The audio-recordings will be transcribed and analyzed as described in the focus group guide. Information from the focus groups will help inform the physician training curriculum for the physicians in the PCCS-WLM program (Comparator 1). The audio-recordings of the focus groups will be destroyed 5 years after these recordings are made and will be stored in a locked file cabinet in the Psychology Building at the University of Florida's Gainesville campus until they are destroyed. The PI, Co-PIs, Co-Is and other study staff as well as a hired transcription company will have access to the audio recordings for transcription purposes only. After the transcriptions are made, the PI, Co-PIs, Co-Is and other staff will have access to the audio-recordings until they are destroyed. The audio-recordings will be destroyed by Shred-it—a UF authorized Destruction and Disposal Services Company.

**Physician Training for Implementing the Weight Loss Maintenance Programs.** Prior to beginning either of the physician-implemented weight-loss maintenance programs, the physicians who deliver each program will receive training on how to implement the program that will be provided in their respective clinic. The physician training time for implementing the PCCS-WLM program (Comparator 1) will be the same as the physician training time for implementing the SB-WLM program (Comparator 2). All of the physicians, regardless of which program they implement at their clinic, will experience the following in this order: (a) completion of the Tucker Culturally Sensitive Health Care Inventory – Provider Version, (b) 4-hour training that will include a 3-hour in-person training and a 1-hour on-line training, (c) 3 booster training sessions (in person and online), scheduled to occur at quarterly intervals (i.e., just prior to each quarterly physician-patient weight loss maintenance program visit), and (d) completion of the Tucker Culturally Sensitive Health Care Inventory – Provider Version at the end of the study. We will also implement a satisfaction survey for the physicians regarding the weight loss maintenance phase (i.e., at month 18). [name] will lead the training for the physicians who will implement the PCCS-WLM program (Comparator 1), and [name] will lead the training for the physicians who will implement the SB-WLM (Comparator 2). In all of these trainings, the physician trainees will be instructed to remind their patient participants of the importance of reaching and/or maintaining the health-smart goal of reducing their body weight at least 5% from when they began the earlier 6-month Health-Smart program.

**Description of the PCCS-WLM program (Comparator 1).** This program is designed to enable physicians to: (a) talk with their Black women patients about their weight, weight loss goals and goal barriers, and strategies for overcoming their goal barriers, and deliver this talk in patient-centered, culturally sensitive ways (i.e., in ways that enable Black women patients to feel comfortable with, trusting of, and respected by the physicians talking with them), (b) assist their patients with engaging in self-identified strategies for achieving and sustaining their self-selected health-smart goals for weight loss and overall health, (c) be knowledgeable about health-smart behaviors (healthy eating

and drinking, physical activity, and managing stress/anxiety, and depression), (d) use behaviors and display attitudes in physician-patient interactions with Black women patients that are provider cultural sensitivity indicators in published literature, but customized for use when counseling Black women patients with obesity—customized based on operationalization of these indicators by the Black focus group participants who were asked to identify specific ways to show these indicators when talking with Black women with obesity about their weight and weight loss, and (e) say and display behaviors and attitudes that Black women in the aforementioned focus groups identified as important when discussing obesity and losing weight with Black women patients who have obesity.

**Description of the SB-WLM program (Comparator 2).** This program is designed to enable physicians to: (a) implement motivational interviewing approaches when talking with their patients about their weight loss goals and behavioral strategies to achieve these goals, (b) become knowledgeable about empirically supported behavioral change principles that have been used to help patients maintain weight loss in previous interventions, (c) communicate how to use these empirically supported behavioral change principles to have patients initiate or maintain their self-selected health-smart goals related to weight loss and/or weight loss maintenance, and (d) use motivational interviewing approaches to communicate empathy and understanding with patients who are struggling to maintain their weight loss and/or accomplish a behavioral goal.

**External Control Monitoring to Verify that the Physicians and CHWs are Following Provided Training.** This external control monitoring will occur during the CHW integration period, the CHW implementation of Health-Smart, and the physician weight loss maintenance year. The CHW monitoring will be conducted by undergraduate student researchers in a research lab course taught by the PI and from among the study staff—all of whom will be trained to conduct this monitoring. This external control monitoring will involve observing health-smart group sessions, either in person or through teleconferencing, that are run by CHWs and using a monitoring form to rate whether or not the activities of the sessions were implemented by the CHWs. The study staff, either in person or through the telemedicine system, will observe the physicians to monitor fidelity to the weight maintenance program that they were trained to implement.

**Measurement Session 3.** After the completion of the quarterly physician visits, patients will have their weight, height, blood pressure, blood glucose, Hemoglobin A1c, and lipids measured again as well as complete the questionnaires previously completed at Measurement Sessions 1 and 2. The research coordinators assigned to clinics will input the patients' biometric and lab data from Health Data Log form and store it in the Dedicated Research Drive.

**Participant Questionnaires/Instruments.** The following tools will be administered during the measurement sessions. Most of these questionnaires will be completed at each measurement period except the following that will only be administered at the 2 and 3rd measurement period: Health-Smart Participant Satisfaction Questionnaire, Patient Survey of Provider Weight Management Practices, Patient Satisfaction Questionnaire – 18, and Tucker Culturally Sensitive Health Care Inventory – Patient Version. The questionnaires will be filled out electronically on a computer or tablet using Qualtrics and stored in a secure UF server. The survey data will include a patient identification number for tracking purposes. No PHI or medical records including lab results will be stored in Qualtrics, only patient

satisfaction and perceptions information. A CHW will be present when each patient is completing the questionnaires and will provide each patient with whatever assistance is needed when completing the questionnaires. A paper version will be available for those who cannot complete it online.

Motivators of and Barriers to Health-Smart Behaviors Inventory (MB-HSBI)–Adult Version (Tucker, Rice, Hou, Kaye, Nolan, Grandoit, Gonzales, Smith, & Desmond, 2011). The MB-HSBI—Adult Version is a 129-item inventory that assesses motivators of and barriers to engaging in specific health-smart (health promoting) behaviors within each of the following four domains: (1) Eating a Healthy Breakfast, (2) Eating Healthy Foods and Snacks, (3) Drinking Water and Other Healthy Drinks, and (4) Engaging in Physical Activity. For each of these four domains, the MB-HSBI includes a “Motivators” section that assesses what motivates respondents to engage in the identified health promoting behaviors and a “Barriers” section that assesses barriers to engaging in the identified health promoting behaviors.

International Physical Activity Questionnaire (IPAQ). IPAQ is a 27-item self-report questionnaire that assesses physical activity in five activity domains (job-related, transportation, housework/house maintenance/caring for family, recreation/sport/leisure time, and time spent sitting).

Dietary Short Questionnaire (DSQ, NCI/NHIS CCS 2010 version). The DSQ is a 27-item survey that asks about the frequency of consumption of selected foods and drinks in the past month.

Weight Control Strategies Scale (WCSS). The WCSS is a self-report measure to assess the use of specific strategies for losing weight or maintaining weight loss. The 30-item WCSS contains four subscales: Dietary Choices, Self-Monitoring Strategies, Physical Activity, and Psychological Coping.

USDA Adult Food Security Survey Module (AFSSM). The AFSSM addresses conditions and behaviors related to one’s experience of, and anxiety due to, limited instances and consequences of reduced food intake.

World Health Organization (WHO) Quality of Life–Brief Form (WHOQOL-BREF). This 26-item survey assesses self-reported quality of life, defined by the WHO as “an individual’s perception of their position in life in the context of the culture and value systems in which they live, and in relation to their goals, expectations, standards and concerns.” The questionnaire consists of an overall quality of life question, an overall health question, and questions that assess four quality of life domains (physical health, psychological health, social relationships, and environment); however, only the physical health (7 items) and psychological health (6 items) domain items will be used in this study.

Demographic and Health Information Questionnaire. This researcher-constructed questionnaire is designed to obtain patients’ basic demographic and health information (e.g., age, gender, race/ethnicity, annual household income, highest level of education completed, marital status, employment status, and weight- and obesity-related information and diseases).

Health-Smart Program Evaluation Questionnaire - Participant (6 month and 18 month) – This researcher constructed questionnaire is designed to measure the participants’ satisfaction with the Health-Smart Program. These will be administered at Measurement 2 and 3 time periods.

General Satisfaction subscale of the Patient Satisfaction Questionnaire-(PSQ-18). This subscale assesses patients' level of agreement that they view their medical care broadly as perfect and level of agreement that they are dissatisfied with some aspects of their medical care. Items from this questionnaire that will be included in the present study are items 1, 2, 4, 6, 13, and 14.

Tucker-Culturally Sensitive Health Care Provider Inventory-Patient Form (T-CSHCPI-PF). The T-CSHCPI-PF is a 27-item inventory that will be used to assess patient participants' perceived level of provider patient-centered cultural sensitivity. This inventory is comprised of three sub-scales: (1) Competence/Confidence, (2) Sensitivity/Interpersonal Skill, and (3) Respect/Communication.

Patient Survey of Provider Weight Management Practices. This is an 18-item survey developed by the Oregon Rural Practice-based Research Network and the Oregon Health & Science University in collaboration with the Agency for Healthcare Research and Quality. Two items from the 18-item Patient Survey of Provider Weight Management Practices (items 8 and 13) will be used to measure participants' perceived levels of their physician's engagement in discussions of their weight and health behaviors.

Table 2 lists the measures that will be completed at each Measurement Session.

Category	Intervention-Phase Month		
	0	6	18
Informed Consent and Eligibility criteria	X		
Body weight (Primary outcome)	X	X	X
Patient Goals setting		X	
Physiological Measures		X	X
Lifestyle Change Behaviors		X	X
Psychological Measures		X	X
Measures of patient participants' satisfaction with Health-Smart			X

**CHW Integration.** To address the **third primary aim**, we will implement and evaluate the medical assistant led (MA-led) program designed to integrate the CHWs into the health care team so that these CHWs can implement the 6-month Health-Smart weight-loss program at these clinics. The Office Manager and MAs at each participating clinic will train and mentor the CHWs assigned to that clinic to become integrated into the health care team at that clinic. This training will be informed by the nationally recognized TeamSTEPPS Program^26—an evidence-based set of teamwork strategies and tools developed by the Agency for Healthcare Research and Quality and aimed at optimizing patient outcomes by improving communication and teamwork skills among health care professionals. CHW integration effectiveness will be assessed using ratings by CHWs, MAs, and physicians on the TeamSTEPPS Medical Office Survey of Patient Safety. In particular, two subscales from this survey (the Working in Your Medical Office subscale, and the Communication and Follow-up subscale) will be administered electronically using Qualtrics at the beginning of the project prior to TeamSTEPPS training and after the 6-month Health-Smart weight-loss program. The survey will be anonymous and no personal health information is collected.

**Compensation.** Participating patients can receive up to \$150 in gift cards by participating in each of the three Measurement Sessions. Specifically, they will receive a \$25 gift card after participating in the first Measurement Session (Baseline), a \$50 gift card six months later after participating in Health-Smart and the second Measurement Session (Month-6), and a \$75 gift card 12 months later after participating in the weight loss maintenance sessions with their physician and the third Measurement Session (Month-18).

**Participant Safety.** The data taken during the measurement sessions will also be used for safety measures. If a BP measurement is taken that is an alert value, as listed in the Table 3 below, repeat measurements will be taken per clinic protocol. An average of at least two measurements will be used to determine the appropriate plan of action. The machine that measures blood pressure often also provides a pulse rate reading. The patient's pulse rate is not an outcome measure in the study, but will be addressed if it is outside of the normal range. Total cholesterol, LDL- cholesterol, HDL-cholesterol, triglycerides, and HbA1c will be assessed through point of care (POC) testing, as specified in the Study Intervention section above. Based on the readings of these measurements, an appropriate plan of action will be taken. Table 3 below lists both Urgent (notify PCP within 24 hours) and Alert values (notify PCP immediately while patient is still in the office). If the patient has a result in the alert value range, the physician or non-physician provider will determine if 911 needs to be called.

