**Participant Recruitment:** Participants will be recruited from the UF Jacksonville primary care network. At least 20 of these primary care clinics will be targeted for recruitment of eligible participants, and a multi-faceted approach will be used for recruitment. At the participating clinics, recruitment will involve distribution of marketing materials (e.g., posters and flyers) in the waiting room and exam rooms. These marketing materials will include a telephone number to call if interested in the study. The participating provider in each clinic may also discuss the trial with any potentially eligible patients if they already have an appointment during the recruitment period. If a patient is initially interested in participating and appears to be eligible, the medical staff will ask the patient to complete a short form indicating that she would like to be contacted by a study team member to learn more about the trial. Additionally, to systematically identify and recruit potentially eligible participants, the research team will conduct an IRB-approved query of the UF Health-Jax electronic medical record system (Epic), and organize targeted mailings of a study participation invitation letter to potentially eligible patients (based on their age, race, sex and BMI). The letter will provide an overview of the study and the phone number to call if they are interested in participating in the study.

**Screening.** A trained research coordinator or CHW will receive the phone calls from patients who are interested in participating in the trial and will perform a screening interview after having received verbal consent from the possible patient participant (interested caller). See copy of the screening script and interview tool. If the caller meets the screening criteria and is interested in participating in the study, a visit with their physician or physician extender (ARNP or Physician Assistant) will be scheduled to ensure there are no medical contraindications to their participation in the study. This screening visit will include a review of the patient's medication inventory, medical and hospital admission history for any exclusion criteria noted above as well as a physical exam that includes measuring blood pressure, radial pulse, and weight, administering a mini-cognitive assessment, and reviewing

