the patient's health history. At the end of the screening visit, patients will be informed whether or not they qualify for the study. It is estimated that approximately 1,600 individuals will need to be screened in order to enroll 758 participants. Participants will be enrolled in 3 waves: Wave 1 will include 7 clinics averaging 34 enrollees each, Wave 2 will have 6 clinics with an average of 40 enrollees each, and Wave 3 will include 7 clinics with an average of 40 enrollees per clinic. See Table 1 for wave timing.

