## 5. Statistical Analysis

The primary outcome is change in body weight (weight loss and maintenance of weight loss) in BW patient participants at the 20 participating primary care clinics. The unit of randomization will be the primary care clinic. Each clinic will be randomized into one of the two weight loss maintenance conditions (PCCS-WLM and SB-WLM).

**Sample Size/Power.** To detect a weight-loss difference of 5 pounds (between two groups) with a standard deviation of 12.5 pounds with 80% power and a 5% significance level, we will include 20 clinics and 25 study participants per clinic. Based on our pilot data, an intra-class correlation of 0.05 among patients within a clinic is used in these calculations. Based on the power calculation above, a total of 500 participants (20 clinics x 25 patient participants per clinic) will be needed for final analyses. Assuming a 25% dropout rate of patients per clinic, we will need 34 patients per clinic; thus, 680 patients will be enrolled in the study. However, based on Wave 1 (which involves 7 clinics) patient participant drop-out rate, the number of participants per clinic will need to be increased for Wave 2 and 3 to an average of 40 patients per clinic. Thus, the maximum number of patient participants enrolled in the study will be 758. Consequently, each of the two study arms will have a maximum of 379 patient participants.

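### Clinic allocation has no stated restriction by enrolment wave, the model has no wave term, and nothing says allocation is withheld from the physicians who clear patients until enrolment closes

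*Combined protocol and SAP*

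**What the plan says.** Section 4 (Weight Loss Maintenance Support from Primary Care Physician) states that "The clinics will be randomly assigned to one of these two programs". The PCCS-WLM program "will be implemented by the physicians of the participating patients at 10 clinics in this study", and SB-WLM runs at ten others. Section 5 adds that "The unit of randomization will be the primary care clinic" and that "Each clinic will be randomized into one of the two weight loss maintenance conditions". That is all the plan says about allocation. It gives no sequence method, stratification or concealment, and no date of allocation relative to a clinic's enrolment.

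Entry is staggered. The Screening text in section 4 says that "Participants will be enrolled in 3 waves". For the sizes of the first two it gives "Wave 1 will include 7 clinics averaging 34 enrollees each, Wave 2 will have 6 clinics with an average of 40 enrollees each"; the last is again 7 clinics, at 40. Section 5 (Sample Size/Power) explains that the target per clinic rose after Wave 1 because of Wave 1 drop-out. The model under Data Analysis has two levels, patient and clinic, with no term for wave or calendar time.

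On who knows what, section 4 blinds patients and CHWs; physicians are not listed. Under Participant Recruitment, "The participating provider in each clinic may also discuss the trial with any potentially eligible patients". A physician or physician extender then holds the screening visit, and clearance comes before consent. The only timing given for arm-specific training is "Prior to beginning either of the physician-implemented weight-loss maintenance programs, the physicians who deliver each program will receive training".

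**The concern.** There are two separate gaps.

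**Wave balance.** With only 20 units to allocate, an unrestricted draw often leaves a wave lopsided. Any difference between waves in 6-to-18-month weight change (season, CHW experience, the altered enrolment target) then enters the arm contrast, and the model has no term to take it out.

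**Timing of allocation.** The physicians whose clinics are randomised also help refer and clear patients, and some entry criteria need judgement, such as a serious condition likely to affect weight. If a clinic's arm were known while it was still enrolling, blinding of patients and CHWs would not prevent differential clearance. Both arms share the first 6 months and arm-specific training is needed only before maintenance, so nothing stated requires allocation before a wave has finished enrolling.

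**Working it through.** **Inputs.** From section 5: difference 5 lb, SD 12.5 lb, ICC 0.05, 20 clinics of 25 evaluable patients, 80% power, 5% significance (two-sided assumed). From section 4: waves of 7, 6 and 7; ten clinics per arm. Wave effects are not in the documents and are an assumption.

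**1. The plan's own figure.**
- Design effect = 1 + 24 × 0.05 = 2.2.
- SE of the arm difference = 12.5 × √(2 × 2.2 / 250) = 1.66 lb.
- Power is 85.4% by the normal approximation and 81.4% by noncentral t on 18 df. Nine clinics per arm would give 76.6%, so ten per arm is reproduced.
- Enrolment: 7×34 + 6×40 + 7×40 = 758, as stated.

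**2. Wave balance under one unrestricted 10:10 draw.** If a, b and c are the clinics of Waves 1, 2 and 3 in one arm, P(a,b,c) = C(7,a)·C(6,b)·C(7,c) / C(20,10).
- Wave 1 split 5:2 or worse: 35.0%; 6:1 or worse: 5.7%.
- At least one wave split 5:2 or worse (of 7) or 5:1 or worse (of 6): 53.6%.
- Best possible balance in all three waves: 26.5%.

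**3. Effect on the contrast.** Take wave effects of -w, 0 and +w. The accidental arm shift is 0.2w(c − a).
- Var(c − a) = [10×10 / (20×19)] × 14 = 3.68, so the SD of the shift is 0.2w × 1.92 = 0.38w.
- P(|c − a| ≥ 3) = 19.2%. The shift is then at least 0.6w.

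**4. How large w can be.** These effects over 7, 6 and 7 clinics have variance (14/20)w² = 0.7w². The plan's total between-clinic variance is 0.05 × 12.5² = 7.8 lb². If that total includes wave differences, w is at most √(7.8/0.7) = 3.3 lb. The shift SD is then:
- w = 2: 0.77 lb
- w = 3.3: 1.27 lb

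**5. Overlap with the planned SE.** The SE² is 2.75, of which 2 × 7.8/10 = 1.56 is between-clinic. At w = 2 the wave part of the between-clinic variance is 0.7 × 4 = 2.8 of 7.8 lb², or 36%. At w = 3.3 it is nearly all of it. The shift is therefore not an additional error on top of 1.66 lb.

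**6. Cost and gain of a wave term.**
- Waves do not differ: 16 df in place of 18 gives 80.8% against 81.4%. This charges only the df. A 4:3, 3:3, 3:4 split also gives Σn₁n₀/n = 12/7 + 9/6 + 12/7 = 4.93 against 5, so SE = 1.66 × √(5/4.93) = 1.67 lb and power is 80.2%.
- Allocation already lopsided at 5:2, 3:3, 2:5: the sum is 10/7 + 9/6 + 10/7 = 4.36, SE is 1.78 lb and power is about 75%.
- Waves differ with w = 2 and balance is kept: SE² falls by 2 × 2.8/10 = 0.56 to 2.19, SE is 1.48 lb, and power is about 88%.

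**The case against.** The strongest reply is that silence is not a statement. The plan nowhere says that allocation is unrestricted, that all 20 clinics are drawn at once, or that any physician learns the arm before screening ends. **This stands.** A reader might infer that clinics are randomised in disregard of waves and that physicians screen knowing their arm; the text supports neither. The 35% and 54% figures are conditional on a single unrestricted draw.

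Second, chance imbalance under randomisation is a matter of efficiency, and the design effect already carries between-clinic variance. **This also stands.** Full confounding of arm with wave is impossible with 10:10 and waves of 7, 6 and 7. Setting the shift beside 1.66 lb as a separate threat would count it twice. Wave effects of 4 lb either side would imply 0.7 × 16 = 11.2 lb² between waves, more than the 7.8 lb² the plan allows for all clinic differences, so that case is left out.

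Third, the selection route is narrow. Invitations also go out from a record query, a coordinator or CHW does the telephone screen and takes consent, an extender may hold the screening visit, and both arms share the first 6 months. No motive for clearing patients differently by arm is evident. **This reduces the risk but does not remove it**, since physician clearance is required and physicians are not listed as blinded.

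Fourth, Wave 1 drop-out has already been used, so a change in allocation may come too late for that wave. This is true, and the fix allows for it.

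What survives is that the stated method leaves out inexpensive protections, and that the model omits wave although the plan changed its enrolment target between waves.

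**Conclusion.** The point holds as a worthwhile, low-cost design improvement, not as a demonstrated flaw. If allocation is one unrestricted draw, a badly split wave is more likely than not (about 54%). The resulting arm shift has SD of about 0.8 to 1.3 lb for w of 2 to 3.3 lb, against a 5 lb target. The range rests on an assumed pattern of wave effects, and its upper end on reading the plan's ICC as total between-clinic variation. The cost is lost precision and a realised imbalance in this one trial; the estimator stays unbiased over repeated allocations. The wave bars in Table 1 cannot be read in the available text, so calendar overlap between waves cannot be judged. Selective clearance is possible on the stated procedures, but there is no evidence that it occurred and no size can be put on it. The sample-size calculation itself is not in dispute.

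**What to change.** 1. **Analysis, all waves.** In section 5 (Data Analysis), add wave as a fixed effect in the arm comparison, specified before arm-level outcomes are seen.
2. **Allocation, waves not yet allocated.** State in sections 4 and 5 that clinics are randomised within wave by a statistician independent of recruitment. From the start this would be 4:3, 3:3 and 3:4. If Wave 1 is already allocated, split the remaining waves as evenly as the 10:10 total permits.
3. **Timing, waves not yet allocated.** Release each wave's allocation only after its enrolment and baseline measurement are complete and before its physician training.
4. **Waves already allocated.** Report how and when allocation was made and who knew it, and apply the wave term only. If wave-restricted, late allocation was always intended, items 2 and 3 amount to writing it down.

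The cost is protocol wording, one model term using 2 df, and a shorter window for scheduling physician training. No change in sample size is needed. The wave term costs more if the allocation already made is lopsided, as shown in the working, which is a reason to restrict the remaining waves.
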